##### **9.4.2 Gastrointestinal Toxicities**

Lansoprazole or another oral PPI is required (H2 antagonists are recommended if subject has intolerance or hypersensitivity to PPI) for the duration of treatment with oprozomib to prevent GI toxicities. In an earlier clinical study (Study 2011-001) the PK exposure of oprozomib (assessed by  $AUC_{last}$  and  $C_{max}$ ) was compared in subjects ( $n = 21$ ) receiving PPIs versus subjects ( $n=45$ ) not receiving PPIs. In this preliminary analysis, PPI did not appear to have any effect on the PK exposure of oprozomib.

Subjects who experience grade 3 or 4 GI hemorrhage during the study will not be re-challenged with oprozomib. Subjects who experience grade 1 or 2 GI hemorrhage may be re-challenged following discussion and agreement between the Amgen Medical Monitor and investigator.

It is strongly recommended that subjects be premedicated with a 5-HT3 antagonist, such as ondansetron or granisetron, prior to each dose of oprozomib and then as needed to prevent nausea and vomiting. Additional antiemetics may be used per investigator discretion.

For subjects developing any grade of diarrhea, loperamide (Imodium) is strongly recommended at the first onset of symptoms. Other antidiarrheal agents may be used if necessary.

#### **9.4.3        Pancreatitis**

Evaluate abdominal pain (particularly  $\geq$  Grade 3 in severity) with nausea, vomiting, and diarrhea with testing of amylase/lipase levels and abdominal imaging, as clinically indicated.

#### **9.4.4        Thrombosis**

Aspirin (or other anticoagulant or antiplatelet medication such as clopidogrel bisulfate, low-molecular-weight heparin, or warfarin) is recommended as prophylaxis for venous and arterial thromboembolism based on assessment of the subject's underlying risk factors (refer to the Pomalidomide Prescribing Information [**Pomalidomide U.S. Prescribing Information for United States; for other countries, see appropriate prescribing information**] for more information).

#### **9.4.5        Tumor Lysis Syndrome (TLS)**

Oral hydration of 1.5–2 liters per 24 hours must be instituted in all subjects 24 hours prior to initiation of therapy for every cycle and continued throughout every day of oprozomib dosing. Premedication with allopurinol or other approved uric acid-lowering agents is highly recommended for subjects with high tumor burden (ie, for multiple myeloma: Durie-Salmon or International Staging System Stage II/III, or rapidly increasing M-protein or light chains) or compromised renal function (creatinine clearance [CrCl]  $< 50$  cc/min). These subjects may be at elevated risk for TLS and should be closely monitored. Uric acid levels should be normalized prior to initiation of treatment, if appropriate.

Subjects with laboratory abnormalities prior to dosing that are consistent with lysis of tumor cells must not receive the scheduled dose prior to institution of the aforementioned preventive measures. Evidence of lysis of tumor cells is defined by abnormalities in at least 3 of the following 4 categories:

1. Increase in LDH increase  $\geq$  2 fold from baseline ULN;
2. Increases in serum creatinine, uric acid, or phosphorus  $\geq 50\%$ ;
3. Potassium increase  $\geq 30\%$ ;
4. Calcium decrease from baseline of  $\geq 20\%$  in the absence of concomitant bisphosphonate therapy (Sezer, 2006).

If TLS occurs as defined by the laboratory abnormalities described above, cardiac rhythm, fluid, and serial laboratory monitoring should be instituted. Correction of electrolyte abnormalities, monitoring of renal function and fluid balance, and administration of therapeutic and supportive care, including dialysis, should be done as clinically indicated. In the setting of TLS, oprozomib treatment will be interrupted until resolution of all clinical and laboratory abnormalities consistent with TLS. Once TLS has resolved, the subject can resume treatment at the same dose level. The Amgen medical monitor should be consulted if there is a treatment delay > 4 weeks.

All cases of TLS must be reported to Amgen as an SAE as outlined in Section [12.2.2.2](#).

#### **9.4.6 Orthostatic Hypotension**

Orthostatic hypotension has been reported in subjects taking oprozomib. The following guidelines should be employed in the management of subjects exhibiting orthostatic hypotension. An etiology should be sought for the orthostatic hypotension to determine if its cause is neurogenic, non-neurogenic or iatrogenic.

- For those subjects with orthostatic hypotension who are taking antihypertensives, the subject's dosage and use of antihypertensive agents should be evaluated and reassessed on an ongoing basis while on study.
- Fluid intake should be assessed to confirm the subject is getting appropriate hydration in accordance with protocol requirements of 6 to 8 ounce glasses of fluids in the 24 hours prior to dosing and on every day of oprozomib dosing.
- Fluid status should be evaluated and maintained at normal levels in subjects with orthostatic hypotension.
- If protocol requirements for oral intake of fluids are already being met, additional measures should be taken to increase blood pressure per investigator discretion, such as increased oral intake, floniene or midodrine, others depending on the etiology. Holding the dose and dose reduction upon resolution may be a consideration.
- Ongoing monitoring of fluid status is warranted and should be managed per investigator discretion.
- Evaluate and confirm there is no occult bleeding.
- In addition, vital signs monitoring may be extended beyond the time periods specified in the Schedule of Assessments.

#### **9.5 Hepatotoxicity Stopping and Rechallenge Rules**

Subjects with abnormal hepatic laboratory values (eg, alkaline phosphatase [ALP], aspartate aminotransferase [AST], alanine aminotransferase [ALT], total bilirubin [TBIL] or international normalized ratio [INR]) or signs/symptoms of hepatitis may meet the criteria for withholding of investigational product. Withholding is either permanent or

conditional depending upon the clinical circumstances discussed below (as specified in the Guidance for Industry Drug-Induced Liver Injury: Premarketing Clinical Evaluation, July 2009).

**9.5.1 Criteria for Permanent Withholding of Study Treatment due to Potential Hepatotoxicity**

Study treatment should be permanently withheld and the subject should be followed according to the recommendations in [Appendix A](#) (Additional Safety Assessment Information) for possible drug-induced liver injury (DILI), if ALL of the criteria below are met:

Increased AST or ALT from the relevant baseline value as specified below:

Baseline AST or ALT value	AST or ALT evaluation
< ULN	> 3X ULN

AND

TBIL > 2 x ULN or INR > 1.5

AND

No other cause for the combination of the above laboratory abnormalities is immediately apparent; important alternative causes for elevated AST/ALT and/or elevated TBIL values include, but are not limited to:

- Hepatobiliary tract disease
- Viral hepatitis (eg, Hepatitis A/B/C/D/E, Epstein-Barr Virus, Cytomegalovirus, Herpes Simplex Virus, Varicella, Toxoplasmosis, and Parvovirus)
- Right sided heart failure, hypotension or any cause of hypoxia to the liver causing ischemia
- Exposure to hepatotoxic agents/drugs including herbal and dietary supplements, plants, and mushrooms
- Hereditary disorders causing impaired glucuronidation (eg, Gilbert's syndrome, Crigler-Najjar syndrome ) and drugs that inhibit bilirubin glucuronidation (eg, indinavir, atazanavir)
- Alpha-one antitrypsin deficiency
- Alcoholic hepatitis
- Autoimmune hepatitis
- Wilson's disease and hemochromatosis
- Nonalcoholic Steatohepatitis (NASH) or other "fatty liver disease"
- Non-hepatic causes (eg, rhabdomyolysis, hemolysis)

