### 7.1 Inclusion Criteria

- 101 Subject has provided informed consent prior to initiation of any study-specific activities/procedures
- 102 Age  $\geq$  18 years old at the time of signing the informed consent
- 103 Subject must have a pathologically documented, definitively diagnosed, multiple myeloma relapse, or refractory progressive disease after at least 2 lines of therapy for multiple myeloma (see [Appendix D](#) and [Appendix F](#) for further details). Prior therapeutic treatment or regimens must include a proteasome inhibitor and lenalidomide
- 104 Subject must be willing and able to undergo bone marrow aspirate per protocol (with or without bone marrow biopsy per institutional guidelines)
- 105 Measurable disease (assessed within 28 days prior to day 1), as indicated by one or more of the following:
  - Serum M-protein  $\geq$  0.5 g/dL
  - Urine M-protein  $\geq$  200 mg/24 hours
  - In subjects without detectable serum or urine M-protein: serum Free Light Chain (sFLC)  $\geq$  10 mg/dL ( $\geq$  100 mg/L) and an abnormal sFLC ratio
- 106 Eastern Cooperative Oncology Group (ECOG) performance status of  $\leq$  2
- 107 Hematological function, as follows, without transfusion support:
  - Absolute neutrophil count  $\geq$  1.0  $\times$  10^9/L
  - Platelet count  $\geq$  75  $\times$  10^9/L (in patients with  $<$  50% of bone marrow nucleated cells were plasma cells) or  $\geq$  50  $\times$  10^9/L (in patients with  $\geq$  50% of bone marrow nucleated cells were plasma cells) without transfusion or growth factor support

- Hemoglobin > 8 g/dL (> 80 g/L) Use of erythropoietic stimulating factors and red blood cell (RBC) transfusions per institutional guidelines is allowed, however most recent RBC transfusion must not be within 7 days prior to obtaining screening hemoglobin

108 Coagulation function as follows: PT/INR and PTT < 1.5 x Institutional Upper Limit of Normal (ULN)

109 Renal function as follows: estimated glomerular filtration rate based on Modification of Diet in Renal Disease calculation (MDRD) > 30 mL/min/1.73 m^2

110 Hepatic function, as follows: AST and ALT < 3 x ULN, Total bilirubin < 1.5 x ULN (except subjects with Gilbert's syndrome)

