### **9.5.2 Criteria for Conditional Withholding of Study Treatment due to Potential Hepatotoxicity**

For subjects who do not meet the criteria for permanent withholding of study treatment outlined above and with no underlying liver disease and normal transaminases and TBIL at baseline or subjects with underlying liver disease and baseline abnormal transaminases, the following rules are recommended for conditional withholding of study treatment:

- Elevation of either AST or ALT according to the following schedule:

Baseline AST or ALT value	AST or ALT elevation
Any	> 8x ULN at any time
Any	> 5x ULN but < 8x ULN for ≥ 2 weeks
Any	> 5x ULN but < 8x ULN and unable to adhere to enhanced monitoring schedule
Any	> 3x ULN with clinical signs or symptoms that is consistent with hepatitis (such as right upper quadrant pain/tenderness, fever, nausea, vomiting, jaundice, rash or eosinophilia (> 5%)).

- OR: TBIL > 3x ULN at any time
- OR: ALP > 8x ULN at any time

Study treatment should be withheld pending investigation into alternative causes of DILI. If study treatment is withheld, the subject should be followed according to recommendations in [Appendix A](#) for possible DILI. Rechallenge may be considered if an alternative cause for impaired liver tests (ALT, AST, ALP) and/or elevated TBIL is discovered and the laboratory abnormalities resolve to normal or baseline.

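### Read literally, the Section 9.5 liver stopping rules leave out subjects enrolled with raised AST or ALT and no liver disease

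*Protocol*

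**What the plan says.** **Entry.** Protocol Section 7.1, criterion 110, sets the liver limits at "AST and ALT < 3 x ULN, Total bilirubin < 1.5 x ULN", with Gilbert's syndrome excepted. Nothing there ties a raised transaminase to known liver disease.

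**Scope of the stopping rules.** The introduction to Section 9.5 says that abnormal liver laboratory values, with AST, ALT, "total bilirubin [TBIL] or international normalized ratio [INR]) or signs/symptoms of hepatitis may meet the criteria for withholding of investigational product".

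**Permanent withholding (9.5.1).** All listed criteria must be met together:
- "Increased AST or ALT from the relevant baseline value as specified below". The table beneath has, as supplied, a single row: baseline below ULN, rising above 3 x ULN.
- "TBIL > 2 x ULN or INR > 1.5".
- No other cause immediately apparent.

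**Conditional withholding (9.5.2).** The lead-in applies the rules to subjects who do not meet 9.5.1 and who are either "with no underlying liver disease and normal transaminases and TBIL at baseline or subjects with underlying liver disease and baseline abnormal transaminases". The table rows then give the baseline as Any. The triggers are:
- AST or ALT above 8 x ULN;
- AST or ALT between 5 and 8 x ULN for two weeks or more, or without enhanced monitoring;
- AST or ALT above 3 x ULN with signs or symptoms of hepatitis;
- "OR: TBIL > 3x ULN at any time";
- ALP above 8 x ULN.

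INR does not appear in 9.5.2.

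**The concern.** A stopping rule should reach every subject the eligibility criteria let in. Here the two rules are keyed to baseline status and the keys do not cover all eligible baselines. The subject left out starts with liver tests that are already abnormal, so the subject with less normal tests at entry has weaker written protection than one who starts normal.

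What is at stake is whether a site following Section 9.5 to the letter would have an instruction to hold treatment when such a subject's liver tests rise sharply. Dosing continues until progression or intolerance, so this matters well beyond the 28-day DLT window.

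**Working it through.** The plan gives no figure to reproduce. The check is to apply the two rules, as worded, to every eligible kind of baseline.

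**Step 1: who is reached.** Take liver disease (yes/no), transaminases (below ULN, or raised but under 3 x ULN) and bilirubin (normal, or raised but under 1.5 x ULN): 2 x 2 x 2 = 8 profiles. Section 9.5.1 reaches a profile only if the baseline transaminase is below ULN. The 9.5.2 lead-in reaches it only if (no liver disease and normal transaminases and normal bilirubin) or (liver disease and raised transaminases).

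| Liver disease | Transaminases | Bilirubin | 9.5.1 | 9.5.2 lead-in |
|---|---|---|---|---|
| No | Normal | Normal | Yes | Yes |
| No | Normal | Raised | Yes | No |
| No | Raised | Either (2 profiles) | No | No |
| Yes | Normal | Either (2 profiles) | Yes | No |
| Yes | Raised | Either (2 profiles) | No | Yes |

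Two of the 8 profiles are outside both rules: raised transaminases without liver disease, whatever the bilirubin. The lead-in also omits 1 + 2 = 3 normal-transaminase profiles, but 9.5.1 reaches those. A baseline exactly at ULN also misses the printed 9.5.1 row.

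**Step 2: what happens on study.** Values are multiples of ULN (INR is absolute), with no other cause apparent.

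| On-study pattern | Baseline ALT 0.8, bilirubin 0.8, no liver disease | Baseline ALT 1.5, liver disease | Baseline ALT 1.5, no liver disease | Same subject, Any rows applied |
|---|---|---|---|---|
| ALT 9 alone, no symptoms | Conditional | Conditional | None | Conditional |
| ALT 9, bilirubin 3.5, INR 2, symptoms | Permanent | Conditional | None | Conditional |
| ALT 4, bilirubin 2.5, no symptoms | Permanent | None | None | None |

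The fourth column is the main point. The last column shows that letting the Any rows govern closes it for the first two patterns.

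**Step 3: the secondary point.** The third pattern gets no hold from a raised baseline even in the last column, because 9.5.2 has no INR term and no laboratory combination of transaminase with bilirubin. This rests entirely on 9.5.1 having no row for baseline at or above ULN.

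**Step 4: why a combined trigger for raised baselines needs care.** Criterion 108 requires "PT/INR and PTT < 1.5 x Institutional Upper Limit of Normal (ULN". The ULN for INR is not stated. Assuming 1.0, 1.1 or 1.2, the permitted baseline INR is below 1.5 x 1.0 = 1.50, 1.5 x 1.1 = 1.65 or 1.5 x 1.2 = 1.80. With a ULN above 1.0, an absolute INR cut of 1.5 could be met at entry. Section 9.4.4 adds that "Aspirin (or other anticoagulant or antiplatelet medication such as clopidogrel bisulfate, low-molecular-weight heparin, or warfarin) is recommended as prophylaxis", so INR may also be raised on purpose.

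**Step 5: likely frequency.** Section 5.3 does not list hepatotoxicity among oprozomib's important identified risks. Table 1 (Section 5.5.5) shows no hepatic DLT in 52 evaluable subjects. The one-sided 95% exact upper bound is 1 - 0.05^(1/52) = 5.6%. That bounds hepatic DLTs in the DLT period for all 52 subjects together; it does not estimate the rate in subjects with raised baselines.

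**The case against.** **Other routes to a hold exist.** Section 9.3.2.2 allows all three drugs to be interrupted for up to 4 weeks for treatment-related toxicity. Section 11.3.1 allows removal for a safety concern, and Section 12.1.2 leaves removal for an adverse event to the investigator. The dose-modification diagrams are not shown in the supplied text and may specify further holds. This stands, and it confines the point to Section 9.5. The printed routes, however, permit a hold and do not require one.

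**Nobody goes unwatched.** Appendix A requires close observation of anyone with AST or ALT above 3 x ULN, whatever the baseline. Sections 12.1.3 and 12.2.2.2 bring drug-induced liver injury into 24-hour SAE reporting. A reader might infer that these subjects are unmonitored or cannot be stopped; the documents do not support that.

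**The 9.5.1 table may be incomplete as read.** Its introduction speaks of the relevant baseline value, yet only one baseline appears, which is what a row lost in PDF reading would look like. A reader might infer that the protocol has no combined transaminase-plus-bilirubin or INR rule for raised baselines. The supplied text cannot settle that. The 9.5.2 lead-in is running prose, so its omission does not depend on the table.

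**A sensible site would follow the Any rows.** Probably so, but the lead-in and the rows then contradict each other, and a stopping rule should not rely on which one a site prefers.

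**Conclusion.** The concern holds for the 9.5.2 lead-in. On the literal wording, subjects enrolled with raised AST or ALT and no liver disease are outside both hepatotoxicity rules, and no level of liver-test abnormality triggers a Section 9.5 hold for them. The conclusion uses the printed one-row 9.5.1 table. If a row for baseline at or above ULN exists, those subjects would be reached by 9.5.1 at that row's threshold but would still be missing from 9.5.2.

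The missing combined trigger for raised baselines is conditional on the PDF showing no further row.

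This is a minor patient-safety wording fix. The 2 of 8 profiles are logical cases, not a share of subjects; the documents do not say how many subjects had raised baseline transaminases. No effect on the MTD, the DLT assessment or any endpoint is claimed.

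**What to change.** **Main change.** Remove the liver-disease and baseline qualifiers from the 9.5.2 lead-in, so that its rules apply to all subjects who do not meet the permanent-withholding criteria. Profiles outside both sections fall from 2 of 8 to 0 of 8, and the lead-in then agrees with the Any rows.

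**Conditional change.** Check the 9.5.1 table in the PDF for a row at or above ULN. If there is none, the sponsor should:
- add a combined AST/ALT plus bilirubin or INR trigger for raised baselines, at a threshold it chooses;
- keep the 9.5.1 condition that no other cause is apparent;
- allow for baseline INR, anticoagulants and Gilbert's syndrome;
- state that the Appendix A 24-hour report applies to this combination.

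**Cost.** The main change is one sentence in an amendment. No new tests are needed, since AST, ALT, bilirubin and INR are already in Table 8. The downside is a few more conditional holds. Some may end treatment, because 9.5.2 allows rechallenge only when another cause is found and the values recover. A subject entering near 3 x ULN could also meet the symptom row after a small rise, if nausea or vomiting (each reported in more than 50% of subjects, Section 5.5.5) is judged consistent with hepatitis.

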### **9.5.2 Criteria for Conditional Withholding of Study Treatment due to Potential Hepatotoxicity**

For subjects who do not meet the criteria for permanent withholding of study treatment outlined above and with no underlying liver disease and normal transaminases and TBIL at baseline or subjects with underlying liver disease and baseline abnormal transaminases, the following rules are recommended for conditional withholding of study treatment:

- Elevation of either AST or ALT according to the following schedule:

Baseline AST or ALT value	AST or ALT elevation
Any	> 8x ULN at any time
Any	> 5x ULN but < 8x ULN for ≥ 2 weeks
Any	> 5x ULN but < 8x ULN and unable to adhere to enhanced monitoring schedule
Any	> 3x ULN with clinical signs or symptoms that is consistent with hepatitis (such as right upper quadrant pain/tenderness, fever, nausea, vomiting, jaundice, rash or eosinophilia (> 5%)).

- OR: TBIL > 3x ULN at any time
- OR: ALP > 8x ULN at any time

Study treatment should be withheld pending investigation into alternative causes of DILI. If study treatment is withheld, the subject should be followed according to recommendations in [Appendix A](#) for possible DILI. Rechallenge may be considered if an alternative cause for impaired liver tests (ALT, AST, ALP) and/or elevated TBIL is discovered and the laboratory abnormalities resolve to normal or baseline.

### **9.5.3 Criteria for Rechallenge of Study Treatment After Potential Hepatotoxicity**

The decision to rechallenge the subject should be discussed and agreed upon unanimously by the subject, investigator, and Amgen. Subjects who clearly meet the criteria for permanent discontinuation (ie, no definite alternative cause for the laboratory abnormalities was discovered as described in Section 9.5.1) should never be rechallenged. If signs or symptoms recur with rechallenge, then oprozomib should be permanently discontinued.

## 9.6 Concomitant Therapy

Throughout the study, investigators may prescribe any concomitant medications or treatments deemed necessary to provide adequate supportive care except for those listed in Section 9.9.

Concomitant therapies are to be collected from informed consent through the EOS. Collect therapy name, indication, dose, unit, frequency, route, start date, and stop date.

### Contraception

Females of reproductive potential must commit either to abstain continuously from heterosexual sexual intercourse or to use 2 methods of effective contraception simultaneously (1 highly effective form of contraception—tubal ligation, intrauterine device [IUD], hormonal [birth control pills, injections, hormonal patches, vaginal rings or implants] or partner's vasectomy and 1 additional effective contraceptive method—male latex or synthetic condom, diaphragm, or cervical cap). Contraception must begin 4 weeks prior to initiating treatment and continue during therapy, dose interruptions, and for 30 days after discontinuation of therapy. Reliable contraception is indicated even where there has been a history of infertility, unless this is due to hysterectomy. Females of reproductive potential should be referred to a qualified provider of contraceptive methods, if needed. Additional details are provided in Pomalidomide Risks of Fetal Exposure, Pregnancy Testing Guidelines and Acceptable Birth Control Methods ([Appendix H](#)), Pomalidomide Education and Counseling Guidance Document ([Appendix I](#)), and Pomalidomide Information Sheet for Subjects Enrolled in Clinical Research Studies ([Appendix J](#)).

Females of reproductive potential must have 2 negative pregnancy tests before initiating study treatment. The first test should be performed within 10 to 14 days of study treatment and the second test should be performed within 24 hours before study treatment. Once treatment has started and during dose interruptions, pregnancy testing for female subjects of reproductive potential should occur weekly during the first 4 weeks of treatment. Pregnancy testing should be repeated every 4 weeks thereafter for female subjects with regular menstrual cycles. For female subjects with irregular menstrual cycles,  $\pm$  7 days of a 28-day cycle, pregnancy testing should be performed every 2 weeks. Pregnancy testing and counseling should be performed if a subject misses her period or if there is any abnormality in her menstrual bleeding. Study treatment must be discontinued during this evaluation.

---

Postmenopausal females (> 45 years old and without menses for > 2 years) and surgically sterilized females are exempt.

Male subjects must use an effective barrier method of contraception during the study and for 90 days following the last dose if sexually active with a female of childbearing potential.

Because pomalidomide is present in the semen of male subjects who receive it, they must always use a latex or synthetic condom during any sexual contact with females of reproductive potential and for up to 90 days after discontinuation of study treatment, even if they have undergone a successful vasectomy. Male subjects must agree not to donate sperm while being treated and for up to 90 days after discontinuing treatment.

